9.4.2 Inferential Analysis of Potential VE Modifiers of Interest

Cox proportional hazards models, adjusted for baseline covariates, will be used for analysis. Assessments of vaccine effects within the baseline positive subgroup and within the baseline negative subgroup in the TVC or ATP cohort are valid based on randomization. If M2-FOI is uncorrelated or negligibly correlated with treatment assignment in the ATP cohort, assessments of vaccine effects separately within categories of M2-FOI = 0 and M2-FOI > 0 in the ATP cohort are approximately valid based on randomization, and there is minimal risk of post-randomization selection bias induced by subsetting on M2-FOI = 0 vs. M2-FOI > 0. Given that few participants with M2-FOI > 1 had first new malaria infection endpoints, statistical inferences studying M2-FOI analyze M2-FOI as a dichotomous variable $I(M2\text{-FOI} > 0)$, interpreted as whether an intercurrent new malaria infection occurred after the first vaccination and by the third vaccination.

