2 RANDOMIZED TREATMENT ARMS

This study is an ancillary study of the GlaxoSmithKline (GSK) RTS,S/AS01E Phase IIb randomized trial (Study Number 204889) that is performed across both study sites Agogo and Siaya. The original randomized trial (MAL-094) vaccinates approximately 1,500 subjects 5-17 months of age in multi-centers according to the following groups:

(GP1) Control group, i.e., rabies vaccine at Month 0, Month 1, Month 2;

(GP2) Group R012-20 - a course of RTS,S/AS01E full dose at Month 0, Month 1, Month 2, and a full dose at Month 20;

[figure not shown]
(GP3) Group R012-14-mD - a course of RTS,S/AS01E full dose at Month 0, Month 1, Month 2, and yearly full doses at Month 14, Month 26, Month 38;

(GP4) Fractionated (Fx) Group Fx012-14-mFxD - a course of RTS,S/AS01E full dose at Month 0 and Month 1, followed by RTS,S/AS01E 1/5th dose at Month 2, Month 14, Month 26, and Month 38.

(GP5) Group Fx017-mFxD - a course of RTS,S/AS01E full dose at Month 0 and Month 1, followed by RTS,S/AS01E 1/5th dose at Month 7, Month 20, and Month 32.

A total of 300 subjects are randomly allocated to each treatment group (Figure 1 below from the MAL-094 protocol).

Figure 1. MAL-094 protocol describing study arms and study visits

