3 STUDY COHORTS

Analyses will be conducted in two distinct study cohorts:

(Cohort 1) The According-To-Protocol (ATP) cohort includes all participants who received the first three vaccinations according to the MAL-094 protocol procedures and who are observed to be at risk for a molecularly confirmed malaria infection at 14 days post-Dose 3.

(Cohort 2) The Total Vaccinated Cohort (TVC) is all participants who received at least one dose of a study vaccine.

Primary and exploratory analyses of vaccine efficacy will be conducted both in ATP and TVC cohorts, with participants analyzed according to the as-treated principle (i.e., actually received treatments). The same ATP cohort will be analyzed in vaccine efficacy analyses of both primary study endpoints defined in Sections 5.1.4 and 5.1.5.

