Herein, we define baseline parasite positivity as either molecular (≥ 325 read threshold) or microscopic detection of parasite positivity in the sample collected on the day of the first vaccination. We define month 2 force of infection (M2-FOI) as an individual's number of new molecular infections detected *after* the first vaccination visit and no later

than at the month 2 scheduled visit (i.e., M2-FOI measures the number of intercurrent new infections post-first-vaccination by the month 2 visit).

Post-hoc analyses presented in this section aim to address four separate exploratory scientific questions:

1. Did baseline parasite positivity modify VE against the first new molecular infection?
2. Did baseline parasite positivity modify VE against the first new clinical malaria episode?
3. Did M2-FOI modify VE against the subsequent first new molecular infection?
4. Did M2-FOI modify VE against the subsequent first new clinical malaria episode?

We will investigate whether and how each of baseline parasite positivity and M2-FOI variables modified the effect of RTS,S vaccination on (i) the time to the first new molecular infection, and (ii) the time to the first new clinical malaria episode meeting the MAL094 protocol's primary case definition.

Questions 1. and 2. will be addressed in both the TVC and ATP cohorts, while questions 3. and 4. will be addressed in the ATP cohort only, given that M2-FOI is measured at the M2 visit (after randomization).

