All models fit to data pooling over both sites will have a separate baseline hazard function for each site. All models will be fit in parallel for the first new molecular infection endpoint and the first new clinical malaria endpoint.

Cox models will be fit to assess hazard ratio-based VE (RTS,S/control) separately within subgroups defined by $M2\text{-FOI} = 0$ and $M2\text{-FOI} > 0$, with 95% Wald CIs, and to generate treatment \times $I(M2\text{-FOI} > 0)$ two-sided interaction Wald test p-values for the following comparisons in the ATP cohort:

- RTS,S regimens GP2–4 pooled (i.e., excluding GP5) vs. the control regimen (GP1) for both combined and individual study sites in the ATP cohort. GP5 is excluded from the RTS,S pooled group in the ATP analysis because the post-dose-3 ATP follow-up period in GP5 is delayed until M7.5–19, whereas, for all other groups including the control group, the follow-up period is M2.5–14. The exclusion of GP5 in the ATP analysis of pooled RTS,S vs. control is of little concern because we hypothesize that neither baseline positivity nor M2-FOI are likely to impact VE during a follow-up period starting 7.5 months after baseline. In addition, GP5 vs. control VE modification during the M7.5–19 period is evaluated separately as specified in the next bullet.
- Each individual RTS,S regimen (except ATP GP2–3 pooled) vs. the control regimen pooling over the study sites as summarized in the following table:

Analysis Cohort	Study Group and Follow-up Comparison
ATP	GP2 + GP3 pooled M2.5-14 vs. GP1 M2.5-14
	GP4 M2.5-14 vs. GP1 M2.5-14
	GP5 M7.5-19 vs. GP1 M7.5-19

The ATP cohort analyses will consider the follow-up period from 14 days after the 3rd dose through the scheduled visit at 12 months after the 3rd visit for each of GP1–5.

In addition to the models described above, we will fit model M5-ATP for the GP2–4 vs. GP1 treatment comparison for the follow-up period restricted to 14 days to 4.5 months after the 3rd dose for assessments of VE modification during a period of potentially limited waning of overall VE against the first new infection.

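### M2-FOI is interpreted as infection by the third dose, which is false for GP5 (third dose at Month 7), so the GP5 row can speak only to infection by Month 2

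*SAP*

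**What the plan says.** SAP Section 9.4 defines the variable by calendar visit: "M2-FOI measures the number of intercurrent new infections post-first-vaccination by the month 2 visit". Section 9.4.2 dichotomises it and says I(M2-FOI > 0) is "interpreted as whether an intercurrent new malaria infection occurred after the first vaccination and by the third vaccination". No arm is excepted from that statement.

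Section 2 gives the schedules. The control arm is described as "Control group, i.e., rabies vaccine at Month 0, Month 1, Month 2", and GP2–GP4 also have their third dose at Month 2. GP5 receives full doses at Months 0 and 1, "followed by RTS,S/AS01E 1/5th dose at Month 7, Month 20, and Month 32", so its third dose is at Month 7.

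Section 9.4.2.2 specifies model M5-ATP with treatment, I(M2-FOI > 0), their interaction and M2-mal-tx. M2-mal-tx is an antimalarial-treatment indicator whose window also closes at the Month 2 visit. The comparisons listed for this analysis include "GP5 M7.5-19 vs. GP1 M7.5-19". The same section explains that GP5 is left out of the pooled vaccine group since its follow-up after Dose 3 begins later, and it plays down the omission on this ground: "we hypothesize that neither baseline positivity nor M2-FOI are likely to impact VE during a follow-up period starting 7.5 months after baseline". It then points to the separate GP5 row as the place where GP5 is evaluated.

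**The concern.** Under the Section 9.4.2 wording, the GP5 interaction test would be reported as addressing whether infection during the priming series modifies VE of the delayed fractional schedule. For GP5 the modifier stops five months before the series is complete. The unmeasured stretch is also the one nearest the third dose.

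Infections detected in that stretch are not picked up elsewhere in the analysis, because follow-up for the GP5 row starts at Month 7.5. The ATP definition in Section 3 requires a child to be "observed to be at risk for a molecularly confirmed malaria infection at 14 days post-Dose 3" and states no exclusion for an earlier infection. A GP5 child first infected at Month 5 can therefore enter the analysis in the M2-FOI = 0 stratum. At stake is what the GP5 row may be said to show, whichever way its result falls.

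**Working it through.** The SAP gives no power, sample-size or misclassification figure for this analysis, so there is nothing to reproduce. The check has two parts.

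**1. Window against schedule (from the SAP alone)**

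| Arm | Dose 3 | M2-FOI window | Months from Dose 1 to Dose 3 covered | Section 9.4.2 interpretation |
|---|---|---|---|---|
| GP1–GP4 | Month 2 | Dose 1 to Month 2 | 2 of 2 | holds |
| GP5 | Month 7 | Dose 1 to Month 2 | 2 of 7 | does not hold |

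For GP5, 5 of 7 months (5/7 = 71%) fall outside the modifier.

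**2. How many M2-FOI = 0 children could be infected in Months 2–7 (illustration)**

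Inputs: the rate r of new infections per year is assumed. Protocol Section 6.2 gives only clinical planning rates, at least 0.5 per year in controls and 0.29 in the standard-schedule groups, and expects infection to be more frequent than clinical malaria. I take r = 0.5, 1 and 2.

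- Constant rate: P(infected in Months 2–7 given M2-FOI = 0) = 1 − exp(−5r/12). For r = 0.5, 1 − exp(−0.208) = 0.188.
- Gamma frailty with variance k, to allow children to differ in exposure: S(t) = (1 + k·r·t)^(−1/k), and the probability is 1 − S(7/12)/S(2/12). For r = 0.5 and k = 2, S(2/12) = 1.1667^(−1/2) = 0.926 and S(7/12) = 1.5833^(−1/2) = 0.795, giving 0.142.

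| r per year | No frailty | Variance 1 | Variance 2 |
|---|---|---|---|
| 0.5 | 19% | 16% | 14% |
| 1 | 34% | 26% | 22% |
| 2 | 57% | 39% | 29% |

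Seen from the other side, the share of children infected by Month 7 who are classed M2-FOI = 0 is [P(by M7) − P(by M2)]/P(by M7). Without frailty this is 68%, 65% and 59% at the three rates; for r = 0.5 it is (0.253 − 0.080)/0.253 = 0.68. With frailty variance 2 it is 64%, 58% and 50%.

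**3. What a longer window would do to balance between arms**

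Section 9.4.2 makes the validity of the M2-FOI strata depend on negligible correlation between the modifier and treatment. As an illustration only, apply the clinical planning rates of 0.5 (control) and 0.29 (RTS,S) as constant rates:

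- Counting to Month 2: 1 − exp(−0.5 × 2/12) = 8.0% against 1 − exp(−0.29 × 2/12) = 4.7%, a gap of 3.3 points.
- Counting to Month 7: 1 − exp(−0.5 × 7/12) = 25.3% against 1 − exp(−0.29 × 7/12) = 15.6%, a gap of 9.7 points.

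The longer window matches GP5's schedule but brings more of the vaccine effect into the modifier.

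**The case against.** The variable is named and defined at Month 2, and the numbered questions in Section 9.4 ask about M2-FOI, not about infection before Dose 3. Read that way, the GP5 row answers its question, and a fixed window from randomisation in every arm is a defensible choice. The SAP also leaves GP5 out of the pooled comparison and says in advance that it expects little effect of M2-FOI so late. Models M6-ATP to M8-ATP and the restricted-period fit of M5-ATP are specified for GP2–4 against GP1 only.

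Most of this stands, and it limits the reach of the point. It does not remove the mismatch. The advance hypothesis concerns infections in Months 0–2 and is silent on Months 2–7. The reason given for leaving GP5 out of the pool is its delayed follow-up, not the modifier window. The GP5 row is still run, under an interpretive sentence that makes no exception for it.

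A reader might infer three stronger things that the documents do not support:

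- **That control children are misclassified too.** Their third dose is at Month 2, so M2-FOI = 0 agrees with their own schedule. All that can be said is that, in the GP5 comparison, their Month 2–7 infections are also outside the modifier.
- **That the window makes a null GP5 interaction likely.** No attenuation or power calculation supports this, and nothing in the SAP says how a null would be reported.
- **That M2-FOI should be replaced by a Month 0–7 count.** The third calculation shows the price: GP5 children have had two RTS,S doses for most of that window and controls none.

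**Conclusion.** The stated interpretation of I(M2-FOI > 0) is correct for GP1–GP4 and false for GP5. This follows from the SAP's own definitions and needs no assumption. In the GP5 row the modifier covers 2 of the 7 months of priming, M2-mal-tx has the same limit, and infections in Months 2–7 appear in neither modifier nor outcome.

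The number of children involved is not known from the documents. The 14% to 57% range rests on assumed rates of 0.5 to 2 per year, constant over time, with frailty variance of 0 to 2. It makes no allowance for a vaccine effect in GP5; at 0.29 per year the share would be 11% without frailty.

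The consequence is confined to what may be concluded from M5-ATP in the GP5 against GP1 row of a post-hoc exploratory section. Primary VE and the pooled GP2–4 analysis are unaffected. This is a minor point, worth making because the correction is easy.

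**What to change.** In Section 9.4.2, limit the interpretation of I(M2-FOI > 0) as infection by the third dose to GP1–GP4. In Section 9.4.2.2, label the GP5 row as modification by new infection by Month 2, and state that it supports no conclusion about infection before GP5's third dose. This costs two sentences and no analysis.

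Optionally, add a sensitivity analysis for GP5 against GP1, alongside M2-FOI and not in its place. It would count new infections, and record antimalarial onset, from Dose 1 through the Month 7 visit in both arms. The monthly samples through Month 20 are already sequenced under Tier 1 (Section 5.2), so no new samples are needed. The cost is two new covariates and one more model fit per endpoint. The distributions planned in Section 9.4.1 are for M2-FOI and would not show imbalance in the new count. That count therefore needs its own tabulation by arm, and the Section 9.4.2 condition of negligible correlation with treatment should be rechecked before its strata are interpreted.

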9.4.2.1 Cox Proportional Hazards Analysis for Assessing Baseline Positivity as a VE Modifier

To address scientific questions 1. and 2. stated above, Cox models studying VE modification by baseline positivity in the TVC cohort will be adjusted for treatment group, baseline positivity, treatment \times baseline positivity interaction, and age at enrollment (model M1-TVC). Cox models studying VE modification by baseline positivity in the ATP cohort will include the following independent variables:

- Model M1-ATP: Adjust for treatment group, baseline positivity, treatment \times baseline positivity interaction, indicator of the onset of antimalarial drug treatment between the first vaccination and the month 2 scheduled visit (M2-mal-tx), age at enrollment, sex, and baseline levels of BMI and hemoglobin.

The baseline positivity status was not randomized such that the assessment of effect modification by baseline positivity is susceptible to potential confounding bias by any other covariate associated with baseline positivity and, at the same time, a VE modifier itself. Since M2-FOI may plausibly serve in this role, for the comparison of pooled RTS,S regimens GP2–4 vs. the control regimen GP1 for both individual and combined sites, we will also fit the following nested Cox models to ATP cohort data while controlling for potential confounding by M2-FOI (in addition to controlling for the main effects of M2-mal-tx, age at enrollment, sex, and baseline levels of BMI and hemoglobin):

- Model M2-ATP: Adjust for treatment group, baseline positivity, ordinal M2-FOI, M2-mal-tx, treatment \times baseline positivity interaction, age at enrollment, sex, and baseline levels of BMI and hemoglobin
- Model M3-ATP: Adjust for treatment group, baseline positivity, ordinal M2-FOI, M2-mal-tx, treatment \times baseline positivity interaction, treatment \times ordinal M2-FOI interaction, age at enrollment, sex, and baseline levels of BMI and hemoglobin
- Model M4-ATP: Adjust for treatment group, baseline positivity, ordinal M2-FOI, M2-mal-tx, treatment \times baseline positivity interaction, treatment \times ordinal M2-FOI interaction, baseline positivity \times ordinal M2-FOI interaction, age at enrollment, sex, and baseline levels of BMI and hemoglobin

We will report AIC values of models M1-ATP, M2-ATP, M3-ATP, and M4-ATP for the treatment comparison of GP2–4 vs. GP1 for the individual and combined sites as a way of characterizing the relative quality of the nested models.

All models fit to data pooling over both study sites will have a separate baseline hazard function for each site. All models will be fit in parallel for the first new molecular infection endpoint and the first new clinical malaria endpoint.

Cox models will be fit to assess hazard ratio-based VE (RTS,S/control) separately within the baseline positive and baseline negative subgroup, with 95% Wald CIs, and to generate treatment \times baseline positivity two-sided interaction Wald test p-values for the following comparisons:

- **[TVC analyses]** RTS,S regimens GP2–4 pooled (i.e., excluding GP5) vs. the control regimen (GP1) for both combined and individual study sites in the TVC cohort.
- **[ATP analyses]** RTS,S regimens GP2–4 pooled (i.e., excluding GP5) vs. the control regimen (GP1) for both combined and individual study sites in the ATP cohort. GP5 is excluded from the RTS,S pooled group in both the TVC and ATP analyses because the post-dose-3 ATP follow-up period in GP5 is delayed until M7.5–19, whereas, for all other groups including the control group, the follow-up period is M2.5–14. The exclusion of GP5 in the analyses of pooled RTS,S vs. control is of little concern because we hypothesize that neither baseline positivity nor M2-FOI are likely to impact VE during a follow-up period starting 7.5 months after baseline. In addition, GP5 vs. control VE modification analyses in the TVC cohort during the M0–20 period and in the ATP cohort during the M7.5–19 period are evaluated separately as specified in the next bullet.
- Each individual RTS,S regimen (except ATP GP2–3 pooled) vs. the control regimen pooling over the study sites as summarized in the following table:

Analysis Cohort	Study Group and Follow-up Comparison
TVC	GP2 M0-20 vs. GP1 M0-20
	GP3 M0-20 vs. GP1 M0-20
	GP4 M0-20 vs. GP1 M0-20
	GP5 M0-20 vs. GP1 M0-20

ATP	GP2 + GP3 pooled M2.5-14 vs. GP1 M2.5-14
	GP4 M2.5-14 vs. GP1 M2.5-14
	GP5 M7.5-19 vs. GP1 M7.5-19

The ATP cohort analyses will consider the follow-up period from 14 days after the 3rd dose through the scheduled visit at 12 months after the 3rd visit for each of GP1–5.

In addition to the models described above, we will fit model M1-ATP for the GP2–4 vs. GP1 treatment comparison for the follow-up period restricted to 14 days to 4.5 months after the 3rd dose for assessments of VE modification during a period of potentially limited waning of overall VE against the first new infection (or the first clinical malaria).

9.4.2.1.1 Sensitivity ‘Matching’ Cox Proportional Hazards Analysis Assessing Baseline Parasite Positivity as a Modifier of VE

For further evaluating baseline positivity as a potential VE modifier of interest, we will conduct a sensitivity ‘matching’ ATP cohort Cox analysis which involves stratified sampling, wherein baseline negative participants will be randomly sampled from the same randomization group and study site by matching baseline positive participants on the date of the third dose administration. All models assessing VE of pooled RTS,S (GP2–4) vs. control regimens in the ATP cohort as described in Section 9.4.2.1 will be fit to data from matched random samples, with results averaged across 1000 resampled data sets. The purpose of the matching analysis is to eliminate the possibility that the modifying impact of baseline parasite positivity on VE is confounded by well-timed vaccination at the start of a high-transmission season. This confounding could arise if the baseline positivity status was correlated with calendar time of the third dose administration just prior to the start of a high-transmission season and, at the same time, the effect of RTS,S vaccination on the study endpoint was differential in low- vs. high-transmission seasons.

The matching analysis will use the following stratified sampling design: For each baseline positive participant, m baseline negative participants will be randomly sampled from the same randomization group and study site by matching on the date of the third dose administration, with $m = 1, 2, 3$. The rationale for $m > 1$ is increased precision in estimation of Cox model coefficients by adding hundreds of additional baseline negative matches (the second and third matches). Matching will be performed by prioritizing matches on the exact date of the third dose administration, and only if such matches are unavailable, then the search will be expanded sequentially to ∓ 1 day, ∓ 2 days, ..., ∓ 7 days of the date of the third dose administration. No matching will be considered beyond the interval of ∓ 7 days of the date of the third dose administration. Sampling of m baseline negative matches will be performed without replacement for each baseline positive participant. Across all baseline positive participants, sampling of baseline negative matches will be performed without replacement of sampled matches to other baseline positive participants. A random permutation of baseline positive participants will be used in each iteration to avoid ‘more accurate matching’ of baseline positive participants on the top of the sampling list. To describe the matching accuracy of the

sampling algorithm, a stacked bar plot will be generated for each m showing the proportions of baseline positive participants with matches within intervals of $\mp 0, \mp 1, \dots, \mp 7$ days of the date of the baseline positive participants' 3rd dose administration. The proportions will be reported as sample medians across 1000 replications. For $m > 1$, each baseline positive participant will be assigned to a color-coded category according to the match (among the m matches) sampled from the widest time interval.

Sample medians of estimated hazard ratio-based VEs and confidence interval limits for the baseline positive and baseline negative subgroups as well as treatment \times baseline positivity interaction test p-values will be reported. Besides the sample medians, the whole distributions across the 1000 replications will be plotted.

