- Added Section 9.4 on the post-hoc analysis of modification of RTS,S vaccine efficacy by baseline parasite positivity.

Date: April 7, 2023

SAP version: 1.5

Modifications:

- Section 8: Revised the comparison of all active arms pooled vs. control to be active arms GP2–GP4 vs. control in all ATP sieve analyses in pursuit of exploratory objective 1.
- Section 8.4.2: Clarified one- vs. two-sided hypothesis testing and statistical significance in the following statements:

“For the binary haplotype-level features in (a)–(c), we will estimate genotype-specific hazard-ratio (relative) VE with 95% CIs and a two-sided test for differential genotype-specific (relative) VE using...”

“One-sided testing will be performed for comparisons to the control GP1 regimen of 3D7 Hamming distances, and two-sided testing will be performed for head-to-head RTS,S regimen comparisons of 3D7 Hamming distances as well as for all comparisons of all other quantitative sequence features. Statistical significance is defined as in Section 7.8 except, for multiplicity sets in which one-sided testing is performed, the same definition of FWER and FDR statistical significance is applied to doubled one-sided p-values.”

- Added Section 8.4.3 specifying hypothesis testing multiplicity sets considered in the sieve analysis for primary endpoint 1.

Date: July 31, 2023

SAP version: 1.6

Modifications:

- Revised Section 9.4 to formalize and align statistical analyses with the separate scientific questions about baseline parasite positivity and month 2 force of infection (M2-FOI) as potential VE modifiers of interest.
- Added Section 9.4.2.3 describing a sensitivity analysis to unmeasured confounding.

Date: August 25, 2023

SAP version: 1.7

Modifications:

- Added in Section 9.4 the indicator of the onset of antimalarial drug treatment between the first vaccination and the month 2 scheduled visit as an additional adjustment covariate in the Cox models to control for potential confounding.

CONTENTS

SAP MODIFICATION HISTORY	2
1 SYNOPSIS	8
2 RANDOMIZED TREATMENT ARMS	9
3 STUDY COHORTS.....	11
4 OBJECTIVES	12
4.1 Context for MAL-095 Objectives Relative to MAL-094 Parent Protocol Objectives.....	12
4.2 Primary Objective.....	12
4.3 Exploratory Objectives	13
5 STUDY ENDPOINTS.....	13
5.1 Primary Endpoints.....	13
5.1.1 Definition of New Malaria Infection	13
5.1.1.1 Modified Definition of Molecular Parasite Positivity for Month 32 Analyses 15	
5.1.2 Definition of Primary Endpoint 1	15

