9.4.2.2 Cox Proportional Hazards Analysis for Assessing M2-FOI as a VE Modifier

To address scientific questions 3. and 4. stated above, we will study the indicator $I(M2\text{-FOI} > 0)$ rather than ordinal M2-FOI as a VE modifier because it eliminates the need to model the dose-response association parametrically and pools presumably smaller categories in the right tail of M2-FOI support.

The first Cox model studying VE modification by $I(M2\text{-FOI} > 0)$ in the ATP cohort will include the following independent variables:

- Model M5-ATP: Adjust for treatment group, $I(M2\text{-FOI} > 0)$, M2-mal-tx, treatment \times $I(M2\text{-FOI} > 0)$ interaction, age at enrollment, sex, and baseline levels of BMI and hemoglobin

$I(M2\text{-FOI} > 0)$ was not randomized such that, analogous to Section 9.4.2.1, the assessment of effect modification by $I(M2\text{-FOI} > 0)$ is susceptible to potential confounding bias by any other covariate associated with $I(M2\text{-FOI} > 0)$ and, at the same time, a VE modifier itself. Since baseline positivity may plausibly serve in this role, for the comparison of pooled RTS,S regimens GP2–4 vs. the control regimen GP1 for both individual and combined sites, we will also fit the following nested Cox models to ATP cohort data while controlling for potential confounding by baseline positivity:

- Model M6-ATP: Adjust for treatment group, $I(M2\text{-FOI} > 0)$, baseline positivity, M2-mal-tx, treatment \times $I(M2\text{-FOI} > 0)$ interaction, age at enrollment, sex, and baseline levels of BMI and hemoglobin
- Model M7-ATP: Adjust for treatment group, $I(M2\text{-FOI} > 0)$, baseline positivity, M2-mal-tx, treatment \times $I(M2\text{-FOI} > 0)$ interaction, treatment \times baseline positivity interaction, age at enrollment, sex, and baseline levels of BMI and hemoglobin
- Model M8-ATP: Adjust for treatment group, $I(M2\text{-FOI} > 0)$, baseline positivity, M2-mal-tx, treatment \times $I(M2\text{-FOI} > 0)$ interaction, treatment \times baseline positivity interaction, baseline positivity \times $I(M2\text{-FOI} > 0)$ interaction, age at enrollment, sex, and baseline levels of BMI and hemoglobin

We will report AIC values of models M5-ATP, M6-ATP, M7-ATP, and M8-ATP for the treatment comparison of GP2–4 vs. GP1 for the individual and combined sites as a way of characterizing the relative quality of the nested models.

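### Age at enrollment enters the VE-modifier Cox models only as a main effect, which cannot remove the confounding of effect modification that SAP 9.4.2.1 itself describes

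*SAP*

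**What the plan says.** SAP 9.4 asks, as post-hoc exploratory questions, whether baseline positivity or month 2 force of infection (M2-FOI) modified VE against first new molecular infection and first clinical malaria. The analysis reports VE within subgroups and "two-sided interaction Wald test p-values for the following comparisons".

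Section 9.4.2.1 notes that positivity was not randomized, and names the source of bias as "any other covariate associated with baseline positivity and, at the same time, a VE modifier itself". It then singles out one covariate: "Since M2-FOI may plausibly serve in this role". M2-FOI enters as a main effect in M2-ATP and gains a treatment interaction in M3-ATP and M4-ATP. These models are fitted "in addition to controlling for the main effects of M2-mal-tx, age at enrollment, sex, and baseline levels of BMI and hemoglobin". M1-TVC, the only model for the total vaccinated cohort, has age as its sole further covariate, again as a main effect.

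Section 9.4.2.2 mirrors this for M2-FOI: "Since baseline positivity may plausibly serve in this role", and positivity gains a treatment interaction in M7-ATP and M8-ATP. Age, sex, BMI and hemoglobin get none in any model. The extended models (M2 to M4, M6 to M8) are specified only for pooled GP2-4 versus GP1.

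Section 9.4.1 plots age at enrollment by positivity status and by M2-FOI. The SAP modification history for version 1.7 describes the antimalarial-treatment indicator (M2-mal-tx) "as an additional adjustment covariate in the Cox models to control for potential confounding"; it too is a main effect only.

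**The concern.** On the hazard-ratio scale, a covariate that modifies VE is one with a non-zero treatment-by-covariate term. A main effect absorbs differences in background risk that both arms share. It leaves the treatment-by-covariate part free, and where the covariate differs between positive and negative children, that part loads onto treatment x positivity, the coefficient being tested.

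The SAP uses the right form for M2-FOI and for baseline positivity. It does not use it for age, although it plans to look at whether age is associated with each modifier. At stake is the answer to the four questions in 9.4: positivity or M2-FOI could be reported as modifying VE when some or all of the pattern belongs to age. The single-regimen comparisons and the restricted analysis to 4.5 months after dose 3 rest on M1-TVC, M1-ATP or M5-ATP, where no covariate other than the tested modifier has a treatment interaction.

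**Working it through.** The plan gives no power or error figure for this analysis, so there is none to reproduce. The check asks how large a false interaction a main-effect model returns when positivity truly does not modify VE.

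**Inputs from the documents.** 300 children per arm (SAP 2), so GP2-4 versus GP1 is 900 versus 300 before ATP exclusions; 11.5 months of ATP follow-up (SAP 5.1.4); control and standard-schedule clinical malaria rates of 0.5 and 0.29 per year (Protocol 6.2), hazard ratio 0.29/0.50 = 0.58; two-sided alpha 0.05 (Protocol 6.1).

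**Assumptions, not in the documents.** How positivity and VE vary with age, positivity prevalence, and a second control rate of 1.5 per year.

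**Approximation.** Let RHR be the hazard ratio (vaccine/control) in positives divided by that in negatives; the truth is 1. With two age groups, the false value is roughly

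ln RHR = (share older among positives - share older among negatives) x (ln HR older - ln HR younger).

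The age main effect does not appear. Assuming half the children are in each age group:

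- Weak: positivity 15% younger, 25% older; VE 45% and 35%. Shares older 0.125/0.200 = 0.625 and 0.375/0.800 = 0.469. ln(0.65/0.55) = 0.167. Product 0.156 x 0.167 = 0.026; RHR 1.03.
- Middle: positivity 10% and 30%; VE 50% and 30%. Shares 0.150/0.200 = 0.750 and 0.350/0.800 = 0.4375. ln(0.70/0.50) = 0.336. Product 0.3125 x 0.336 = 0.105; RHR 1.11.
- Extreme: positivity 10% and 35%; VE 55% and 20%. Shares 0.175/0.225 = 0.778 and 0.325/0.775 = 0.419. ln(0.80/0.45) = 0.575. Product 0.358 x 0.575 = 0.206; RHR 1.23.

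**Simulation of these scenarios** (Cox models, 270 control and 810 vaccine children, age as a main effect; ranges cover repeated runs, including control rates of 0.5 and 1.5 per year):

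| Scenario | False RHR | False rejection |
|---|---|---|
| Weak | 1.01-1.05 | about 4-7% |
| Middle | 1.08-1.12 | 5.5-9% |
| Extreme | about 1.20 | about 10-16% |

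In the extreme case, rejection was 9.8% at 0.5 per year and 16.3% at 1.5 per year. Adding treatment x age brought the RHR back to 0.98-1.00.

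**Why rejection rises modestly.** In the middle scenario the interaction SE is 0.21-0.30 on the log scale. The bias is then 0.105/0.30 = 0.35 to 0.105/0.21 = 0.50 standard errors, and the chance of exceeding 1.96 in absolute value is about 6.4% to 7.9%.

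**Second simulation, continuous covariate** (900 versus 300, 1,000 replicates, odds ratio for positivity 2 per SD of the covariate, covariate main effect 0.2):

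| Control rate/yr | Prevalence | VE-modifying log-HR per SD | RHR, main effect | RHR, + treatment x covariate | Rejection, main effect | Rejection, + interaction |
|---|---|---|---|---|---|---|
| 1.5 | 10% | 0 | 0.995 | 0.994 | 5.0% | 5.1% |
| 1.5 | 10% | 0.15 | 1.084 | 0.990 | 6.5% | 5.9% |
| 1.5 | 10% | 0.30 | 1.168 | 0.976 | 10.8% | 4.4% |
| 1.5 | 20% | 0.30 | 1.187 | 0.997 | 15.7% | 5.1% |
| 0.5 | 10% | 0.30 | 1.210 | 1.001 | 7.5% | 4.7% |

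The first row shows that the current form is sound if the covariate does not modify VE. In single large samples of 240,000, adding the main effect barely changed the bias compared with omitting the covariate (for example 1.162 versus 1.149).

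**The case against.** The best defence is that the SAP states a general principle and then acts on the covariates it thinks plausible. M2-FOI and positivity get interactions, dose 3 date is handled by matching within arm and site (9.4.2.1.1), and sites are also fitted separately. The SAP calls the other terms main effects openly and nowhere says that age modifies VE. The whole section is post-hoc and exploratory. All this stands, and it limits the point to a conditional one.

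Three provisions might seem to close the gap for age but do not. Matching is not on age, and the matched samples are refitted with the same models. The unmeasured-confounding analysis (9.4.2.3) takes covariates already in the model as accounted for. The validity by randomization claimed in 9.4.2 concerns VE within each positivity subgroup, not the reason for the difference; for M2-FOI the SAP makes even that depend on negligible correlation with treatment.

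A reader might infer more than the documents support:

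- That subgroup VE, or any primary VE result, is biased. Neither follows.
- That modification by positivity is spurious. The documents report neither the association of age with the modifiers nor any modification of VE by age.
- That sex, BMI and hemoglobin need the same treatment in every model. M1-TVC contains none of them, and 9.4.1 plots only age and vaccination date against the modifiers. Hemoglobin may be a consequence of baseline infection, so conditioning VE on it could remove part of the modification under study.
- That M2-mal-tx should gain an interaction. It is measured after randomization and would need separate justification.

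**Conclusion.** The point holds in conditional form. By the SAP's own definition, a main effect for age does not control confounding of effect modification, and no other planned analysis does so for age. If age both modifies VE and is associated with positivity or M2-FOI, part of the age effect will be attributed to them.

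The size is unknown. The figures above were computed for positivity and rest on assumed contrasts. The upper error rates need both a strong age contrast and an event rate well above the 0.5 per year in the protocol; with a weak contrast the distortion is hard to distinguish from none. What is exposed is the attribution of a subgroup difference in an exploratory analysis. That makes an inexpensive additional model worthwhile, without putting the planned models out of use.

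**What to change.** Refit M1-TVC and M1-ATP to M8-ATP with treatment x age at enrollment added, using the same form for age as in the main effect. Report the modifier interaction estimate, confidence interval and p-value beside the current versions, label the additions post-hoc, and claim modification by positivity or M2-FOI only if it persists. Judge persistence on the estimate as well as the p-value.

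Treatment x sex and treatment x BMI can be added to the ATP models as further sensitivity. Treatment x hemoglobin belongs only in a separate ATP sensitivity model, with its possible dependence on baseline infection stated.

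The change is to model formulas and uses a covariate already in every model. The cost is an interaction SE about 1-5% larger with treatment x age. With treatment x hemoglobin as well, and hemoglobin assumed 0.8 SD lower in positives, the increase was 6-11%, a further reason to keep that model separate.
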